#### **5.3.3 Day 1**

##### **Laboratory testing:**

- creatinine to calculate GFR prior to gadolinium administration (may be done up to 3 weeks prior)

- Urine pregnancy test in women of child bearing potential.

Imaging:

- Anatomical imaging on 3T & 7T and dynamic MRI (with gadolinium, see section 4.1) on either 3T or 7T (dependent on which group subject is assigned and as described in section 5.1.3)
- Day 1 and Day 2 imaging sessions may be separated by up to 7 days.
- A subset of 25 of the 150 subjects will only undergo MRIs on the 7T magnet.

**5.3.4 Day 2**

Imaging

- Anatomical imaging on 3T & 7T and dynamic MRI (with ferumoxytol, see section 4.2). A subset of 25 of the 150 subjects will only undergo MRIs on the 7T magnet.
- Dynamic imaging will be performed on the same scanner as on which the dynamic the dynamic imaging was acquired on Day 1(as described below on Section: 6.0). Ferumoxytol Administration:
  - The ferumoxytol will be diluted 1:2 to make a 10mg/ml solution. The dose of ferumoxytol will be 4 mg/kg (to a maximum of 510 mg), and will be administered intravenously on day 2.
  - Dose 1: Give 1/4th of the total dose (1mg/kg); inject at up to 3 ml/sec followed by a saline flush. This rate is required for adequate signal change during the dynamic imaging.
  - Dose 2: Give 3/4th of the total dose (3mg/kg); inject no faster than 1 ml/sec and followed by a saline flush
  - 
  - The dilution and injection parameters of the ferumoxytol may be adjusted to obtain optimal signal changes on MRI/MRA and to decrease the possibility of an allergic reaction. Injection rate can be varied based on the participant's IV site, but the total dose will never exceed 510mg.

Monitoring

- A clinical examination will be performed before and after the MRI session on Day 2.. Blood pressure and pulse will be monitored before the first dose of ferumoxytol and after each dose of ferumoxytol, and at 30 minutes after the initial dose of ferumoxytol.

**5.3.5 Day 3**

Imaging:

- Post-ferumoxytol MR imaging at both 3T and 7T (as described below in section: 6.0). No contrast agent will be administered on this day. A subset of 25 of the 150 subjects will only undergo MRIs on the 7T magnet.

**5.4 Adverse Events**

Toxicities and adverse experiences will be assessed using the NCI Common Terminology Criteria for Adverse Events v3.0. . Adverse events related to or potentially related to the administration of ferumoxytol will be recorded; adverse events related to

the MRI's experience itself, such as claustrophobia/anxiety, nausea with GBCA injection, or discomfort due to positioning, is not being studied and will not be reported. Adverse events that will be monitored during the infusion include localized discomfort at the IV injection site, pain, respiratory difficulties, flushing, dizziness, pruritis/rash, and any other symptoms that could be secondary to an anaphylactoid type reaction.

#### **5.5 Follow-up:**

The subject will be seen in an outpatient clinic or have a telephone follow up interview approximately 4-6 weeks after the study visit to assess for adverse events.

#### **5.6 Subject Evaluability**

Subjects who are assigned to either the 3T or the 7T magnet strength MRI instruments may not be able to complete the imaging on the assigned strength on a given day. This will most likely be due to an MRI technical issue on the day the subject has been assigned. The 7T MRI is more likely to experience technical difficulties as this is a research instrument and is not a standard clinical product. In addition, a few subjects may not be able to tolerate an MRI examination on a particular day. If one MRI instrument is unavailable and the other one is available, the subject will be "crossed-over" for that day. For Primary Aims 1 and 2, crossing a subject on either day 1 or day 2 (but not both) will mean that the subject will be evaluable for one aim (corresponding to the non-crossover day) but not for the other. The sample size is adequate to allow up to 20% of subjects to be crossed over on at least one day. If one MRI instrument is not available on Study Day 3, data will be collected from that subject on only one instrument and these data will be used only to describe the range of values for that magnet strength.

#### **5.7 Criteria for early termination from the protocol**

- Voluntary subject withdrawal
- Investigator's decision that is in the subject's best interest to withdraw
- Subject becomes pregnant
- Noncompliance
- Significant protocol violation
- For any reason, at the Sponsor or Investigators discretion

### **6 IMAGING SCHEMA AND ACQUISITION**

#### **6.1 Schema**

##### **Day 1**

1. Standard precontrast anatomical MRI sequences at 3T and/or 7T: sagittal T1, coronal FLAIR, MPRAGE, axial T1, T2, T2\*, PD weighted images and DWI.
2. TOF angiography
3. Quantitative T1 images
4. DSC MRI (T2\* weighted) for perfusion with Gd bolus administration dose: 0.1mmol/kg)
5. Quantitative T1 images for permeability measurement will be performed 4 times
6. TOF angiography (postgadolinium)
7. Standard postgadolinium imaging at 3T and 7T: MPRAGE, axial T1, T2, T2\* weighted images.

A subset of 25 of the 150 subjects will only undergo MRIs on the 7T magnet.

[Section 6.1 and 6.2 numbers 4 and 5 will be assigned to either 3 or 7 Tesla. 1, 2, 3, 6 and 7 will be performed on both magnet fields, the order of the scanners will be balanced, see Study Procedures section 5.2.3.] In subjects who cannot tolerate long MRI study either 3T or 7T (MRI with no dynamic imaging) pre-contrast sequences 1, 2 and 3 maybe acquired on Day 2 (dash line in the figure below).

## **Day 2**

1. Standard MRI sequences: axial T1, (MPRAGE, T2, T2\*, PD, DWI images will be acquired only when quality of images are not good or if they were not acquired for some reason in first session)
2. TOF angiography (only when quality of image is not good or was not acquired for some reason on first session)
3. Quantitative T1 images
4. DSC MR (T2\* weighted) for perfusion with ferumoxytol bolus (maximum dose: 1mg Fe/kg) the remaining 3mg/kg to be administered after this series)
5. Quantitative T1 images for permeability measurement will be performed 4 times
6. TOF angiography (post ferumoxytol)
7. Standard MRI sequences (post contrast): MPRAGE, axial T1, T2, T2\* weighted images.

## **Day 3**

1. (24±6h post-ferumoxytol administration in both magnets.)
2. Standard MRI sequences (post contrast): sagittal T1, coronal FLAIR, axial MPRAGE, T1, T2, T2\* weighted images, TOF angiography and Quantitative T1 images.

## 6.2 Schema Options

There are two schema options

[figure not shown]
Duration (min)

### 6.2.1 Option A

Three times in MRI on Day 1 (3T-7T-3T or 7T-3T-7T)	150
One time on MRI scanner Day 2 (3T or 7T)	90
Two times on MRI scanner Day 3 (3T and 7T)	100

### 6.2.2 Option B

Two times on MRI scanner Day1 (3T and 7T)	100
Two times on MRI scanner Day 2 (3T and 7T)	130
Two times on MRI scanner Day 3 (3T and 7T)	100

### 6.3 MR Acquisition Parameters

Images will be acquired at 3T (Siemens TIM) using a 12-channel receive only phased array RF head coil and at 7T (Siemens MAGNETOM) using an 8 channel phased array transmit/receive RF head coil.

#### 3T acquisition parameters:

Scan type	Scan time (min)
0. Setup/localizer/ $B_0$ shimming/ $B_1$ mapping .....	3
1. T1-w sagittal (TE 2.5/TR 300/FA 60) 220mm x 220mm FOV 256 x 256 matrix 4 mm contiguous .....	2
2. FLAIR coronal (TE 9000/TR 95/TI 2500) 230mm x 172mm FOV 256 x 205 matrix 3 mm contiguous .....	4
3.. T1-w axial TSE (TE14/TR700 TSE factor 4 4NEX; PAT=2) 180mm x 240mm FOV 192 x 256 matrix 3 mm contiguous, interleaved .....	4
4. MPRAGE axial (TE 2300/TR 3.4/FA 12) 256 mm x 192 mm FOV 256 x 256 matrix 1 mm contiguous .....	7
5. T2-w axial TSE (TE72/TR9000 TSE factor 9 PAT=2) 180mm x 240mm FOV 192 x 256 matrix 3 mm contiguous, interleaved .....	2
6. PD-w axial TSE (TE14/TR9000 TSE factor 9 PAT=2) 180mm x 240mm FOV 192 x 256 matrix 3 mm contiguous, interleaved .....	2
7. Diffusion weighted MRI axial (TE90/TR6000 SE EPI $b=0, 500, 1000$ s/mm $^2$ ) 220mm x 220mm FOV 128 x 128 matrix 3 mm contiguous, interleaved .....	4
8. MRA 3D-TOF (TE3.2/TR18/FA20; PAT=2) 170mm x 200mm x 150 mm FOV 200 x 400 x 140 .....	5
9. Quantitative T 1 axial (3D GRE TE3/TR15/FA5,20) 180mm x 240mm x 144 FOV 192 x 256 x 48 matrix 3 mm contiguous, 3D .....	5
10. T 2 *-w axial; GEPI (TE25/TR2000/FA50; PAT=2) x 45 volumes 220mm x 220mm FOV 128 x 128 matrix 3 mm contiguous, interleaved .....	6
11. PWI Echo-Planar Gradient Echo and Spin Echo 20- 90 ° Flip Angle TR=2000 msec/TE=28 msec 3mm Slices in Axial Plane .....	3

## **7T acquisition parameters:**

0. Setup/localizer/ $B_0$  shimming/ $B_1$  mapping.....3
1. MPRAGE axial (TE2.7/TR26.5/FA8) 180mm x 220mm x 160mm FOV 320mm x 256mm x 224mm matrix 0.7mm contiguous, 3D .....
2. Quantitative  $T_1$  axial (EPI GRE TE16/TR10000) 256mm x 256mm FOV 128mm x 128mm matrix 2 mm contiguous, interleaved.....
3.  $T_2$ -w axial TSE (TE91/TR10000; ETL 11) 240mm x 180mm FOV 512mm x 384mm matrix 3 mm contiguous, interleaved.....
4. SWI axial (TE12/TR26) 240mm x 180mm FOV 512mm x 384mm matrix 1.5mm contiguous, interleaved.....
5.  $T_2^*$ -w High Resolution axial (TE20/TR950) 220mm x 160mm FOV 960mm x 704mm matrix 1.5 mm contiguous, interleaved .....
6. Diffusion weighted MRI axial (TE90/TR6000 SE EPI  $b=0, 500, 1000$  s/mm $^2$ ) 220mm x 220mm FOV 128 x 128 matrix 3 mm contiguous, interleaved.....
7. DSC:  $T_2^*$ -w axial; GEPI (TE20/TR1500/FA30) x 90 volumes 200mm x 200mm FOV 64mm x 64mm matrix 3 mm contiguous, interleaved.....

**The above detailed sequences are subject to change in order to acquire the best imaging results on the applied field strength.**

## **7 CRITERIA FOR EVALUATION USING MRI**

### **7.1 Lesion assessment methodology and volumetrics**

To be eligible for this study, subjects must have had a radiographically evaluable or measurable lesion on standard MRI. Anatomical images acquired pre- and post contrast, including  $T_1$ -w,  $T_2$ -w, FLAIR, PD images will be assessed. Lesions should be measurable on at least two dimensions. Depending on the MR morphological abnormality of the lesion, volumetric measurement maybe performed using  $T_1$ -w,  $T_2$ -w, FLAIR, PD images. MR signal abnormality refers to:

1.  $T_1$  signal abnormality on precontrast images
2. Abnormal hyperintensity on  $T_1$ -w postcontrast images
3.  $T_2$ /FLAIR signal abnormality

### **7.2 Perfusion MR**

- 7.2.1  $T_2^*$  weighted MR images will be collected during contrast agent administration to obtain a dynamic susceptibility contrast (DSC) data set.
- 7.2.2 Time-intensity curves, cerebral blood volume (CBV) parametric maps and relative CBV (rCBV) values (as area under the signal intensity curve, normalized by area under the curve for control region) will be obtained. Relative mean transit time (rMTT) values will be obtained by gamma variate fitting the time-intensity curves, using Matlab environment

(Mathworks, Natick, MA). The relative perfusion values will be plotted as a function of time with both agents.

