**Table 1** summarizes the measurement parameters that can be extracted from the dynamic imaging studies, with both Gd, and USPIO (28). The observed signal intensity variations in tissue and the blood pool are converted through a log-transformation to  $R2^*$  changes ( $= 1/T2^*$ ). The curves of  $R2^*$  changes versus time for selected tissue regions of interest (ROI) can be fit with a gamma-variate function, to approximate the shape of the first pass peak. The arterial input is used to determine the cut-off point for the fit, i.e. before appearance of the recirculation component. With this fitting procedure, one can determine the mean transit time (MTT). The outcome variable for assessing effects of therapy on tumors will be the cerebral blood volume (CBV) parameter, estimated from  $T2^*$ -weighted DSC MRI with USPIO contrast. We expect USPIO leakage to be minimal during the first pass. CBV is calculated from the area under the curve (AUC) for serial DCE-MRI  $R2^*$  curves, normalized by the  $R2^*$  AUC for an arterial ROI. Cerebral blood flow (CBF) is estimated by model-independent numerical deconvolution of the tissue curves with the arterial input (39, 40). We can also extract the BBB permeability surface area product (PS) from the influx rate constant  $K_i$ , obtained with the Kety-Schmidt model (27, 28). The influx rate constant is related to both CBF and PS, and estimation of PS, therefore requires an independent quantification of CBF (**Table 1**). In addition, one can

use pre- and post-contrast T1 measurements with high spatial resolution (Look-Locker imaging) to determine  $R_1$  ( $= 1/T_1$ ) from before to approx. 10 min. after contrast injection, when the contrast agent has reached a semi-equilibrium. The  $R_1$  changes ( $\Delta R_1$ ) in tissue, normalized by  $\Delta R_1$  in the blood pool, give the blood-brain partition coefficient, which will be measured for Gd contrast, which traverses the BBB relatively rapidly in many tumor types. The partition coefficient for Gd provides a measure of the relative distribution volume for Gd in different tumor types, and can be compared to the CBV (measured with USPIO) to assess the degree of Gd contrast leakage.

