**Table 1. Summary of measurement parameters from dynamic contrast enhancement MRI**

Parameter [Measurement]	Gamma-variate fit [42, 46]	Kety-Schmidt model [21]	Note
MTT [T2*-w DSC]	Calculated from gamma-variate fit to first pass tissue curve; subtract MTT of arterial input for normalization.	n.a.	For intravascular agent, MTT = CBV/flow (central volume principle [30])
CBV [T2*-w DSC]	Tissue first pass AUC, normalized by arterial input curve area [4, 42, 46]	n.a.	In tumors, leakage of Gd may allow CBV quantification only with USPIO
CBF [T2*-w DSC]	Only indirect estimate from CBF = CBV/MTT	Can only determine product of CBF and PS = $K_i$ [21]	Calculated by numerical deconvolution of tissue curves [21, 39, 40]
PS [T2*-w DSC]	PS cannot be estimated with semi-empirical gamma-variate approach	Can only determine product of CBF and PS = $K_i$ [21]	With independent CBF quantification, one can estimate PS from $K_i$ and CBF.
Blood-brain partition coefficient - $\lambda$ [Look-Locker T1 quant.]	Calculated by $R_1$ change in tissue (post-contrast $R_1$ – pre-contrast $R_1$ , normalized by $R_1$ change in blood). Quantification of $V_d$ is not based on any specific model. $\lambda$ can also be obtained from Kety-Schmidt model.		Leakage of Gd contrast is assessed by comparison of $\lambda$ for Gd with CBV

Abbreviations: MTT, mean transit time; DSC, dynamic susceptibility contrast; CBV, cerebral blood volume; AUC, area under curve; USPIO, ultrasmall superparamagnetic iron oxide particles; CBF, cerebral blood flow; PS, permeability-surface area product;  $K_i$ , influx rate constant;  $R_1$ ,  $R_1=1/T_1$

The dynamic MR techniques have been shown to be sensitive to changes in the BBB in animal models (7, 44). Of particular interest, Cha et al. assessed dynamic contrast imaging in a mouse glioma model using a 7T MR scanner (7). MR measurements of relative CBV agreed with histological measurement of microvascular density from the same tumors. This animal study correlated with the observation in our pilot ferumoxytol study that low molecular weight contrast agents such as gadolinium leak rapidly out of the vasculature. Leakage of contrast agent interferes with an accurate determination of CBV and MTT. Our preliminary dynamic MR measurements with ferumoxytol in patients (see section 2.4) show markedly reduced early leakage of the nanoparticles compared to Gd.

[figure not shown]

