In human studies, dynamic MRI has been used to examine hemodynamics in solid tumors, providing *in vivo* data on the vascular pathophysiology and response to treatment

for breast, lung and prostate cancer and is increasingly used in clinical practice (20, 23, 26, 27, 41). Relative CBV (rCBV) maps derived from perfusion MR imaging data provide quantifiable estimates of regional blood volume that can be used to grade gliomas, differentiate different brain tumor types, and distinguish tumors from non-neoplastic lesions, and to assess brain tumor physiology (21). CBV maps and the rCBV values can be calculated in different areas using the ratio between the CBV in the pathological area and in the contralateral white matter. Large, solitary, necrotic metastases can be indistinguishable from high-grade astrocytomas using conventional MRI, but can be distinguished by dynamic contrast MRI (23). Inclusion of dynamic contrast MR imaging as part of a routine evaluation of brain tumors can lead to improved diagnostic accuracy, understanding of tumor pathophysiology, and detection and quantification of tumor angiogenesis. With further work, dynamic MR imaging could be used to assess existing and novel cancer therapies that target blood vessels.

To date, few studies have used USPIO MR contrast agents in dynamic imaging. In one animal study, de Lussanet evaluated a different USPIO (Clariscan NC200150) for dynamic MRI in a mouse subcutaneous colon carcinoma model using a 1.5T scanner (12, 13). They found that USPIO was equivalent to Gd for evaluating the endothelial transfer coefficient surface area product, while USPIO was significantly better than Gd for determining the fractional plasma volume (12, 13). However, it is difficult to draw conclusions from the low resolution images in this 1.5T study. The higher performance gradient systems with increased MR field strength will allow us to improve spatial resolution, while maintaining temporal resolution, and improve image quality because of the higher signal-to-noise ratio with increased field strength.(8, 9) Dynamic MR with USPIO has been reported in human breast cancer (48) and liver metastases (53).

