### **7.3 Vascular Permeability measurement**

$T_1$  weighted MR data will be collected before and after contrast agent administration. Permeability will be evaluated by applying dynamic contrast enhanced (DCE) scans for quantitative  $T_1$  measurements 4 times over 45 minutes and also 24±6 hours after contrast administration. Using the  $R_1$  ( $=1/T_1$ ) values,  $K^{trans}$  will can be calculated in the selected ROIs, (i. tumor core, ii. tumor rim, iii. ipsilateral control region iv. contralateral control region).

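### Section 7.2.2 computes rCBV and rMTT from raw signal curves, while Section 2.3 first log-transforms signal to R2\* change; add that step and name one control region

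*Combined protocol and SAP*

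**What the plan says.** **Section 7.2.2 (Perfusion MR)** is the rule an analyst would follow. It takes rCBV "as area under the signal intensity curve, normalized by area under the curve for control region". For transit time it states: "Relative mean transit time (rMTT) values will be obtained by gamma variate fitting the time-intensity curves". It mentions no logarithm and no R2\* curve, and it does not refer to Section 2.3.

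**Section 2.3** describes a different sequence of steps:

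- "The observed signal intensity variations in tissue and the blood pool are converted through a log-transformation" to R2\* changes.
- The R2\* "changes versus time for selected tissue regions of interest (ROI) can be fit with a gamma-variate function", which leads to the mean transit time.
- "CBV is calculated from the area under the curve (AUC) for serial DCE-MRI" R2\* curves, normalised to an arterial region. Table 1 says the same of CBV: "Tissue first pass AUC, normalized by arterial input curve area".
- Later in 2.3, after Table 1, rCBV is described separately, "using the ratio between the CBV in the pathological area and in the contralateral white matter".

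**Control region.** Section 7.2.2 does not say which control region it means. Sections 7.3 and 7.5 both list two: "iii. ipsilateral control region iv. contralateral control region". Section 7.5 adds that its regions are the ones used for perfusion.

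**Use of the results.** Objective 1.2.2 expects lower blood volume with ferumoxytol than with gadolinium in leaky tumours. Section 9.3 compares the agents on blood volume by repeated measures ANOVA, and Section 9.2 lists CBV and rMTT as the perfusion summaries.

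**Section 7.4** obtains the delayed enhancement volume by multiplying the enhancing pixel area by the pixel volume, and then compares 3T with 7T.

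**The concern.** In a DSC scan the signal falls exponentially with the R2\* change, and blood volume is taken as proportional to the area under the R2\* curve. The area under the signal drop is not proportional to it, because deep drops flatten out. A vascular tumour has a deeper drop than the control region and loses more of its area, so the ratio is pulled towards 1. The same flattening broadens the tumour curve and lengthens its fitted transit time.

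The loss grows with the depth of the drop. If the two agents produce drops of different depth, the same tumour gets two different rCBV values with no difference in biology. That could imitate or hide the agent difference that objective 1.2.2 sets out to describe, and enrolling more subjects would not remove it. An unnamed control region adds a second, avoidable source of variation between readers, agents or magnets.

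**Working it through.** The plan gives no figure of its own on this point, so there is none to reproduce. The check compares what 7.2.2 and 2.3 would return for the same tumour.

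**Inputs.** From the documents: the two calculation rules, and the gamma-variate bolus shape. Assumed, because the documents do not give them: a control-region peak signal drop *d* of 10, 20, 30 or 40%; a true rCBV *R* of 3 or 1.5; equal bolus shape in tumour and control; no leakage and no T1 effect.

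**Model.** Let *g(t)* be a gamma-variate curve scaled to a peak of 1, and let `k = −ln(1 − d)`. Control signal is `S/S0 = exp(−k·g)` and tumour signal is `S/S0 = exp(−R·k·g)`. Three shapes were used (alpha 3, beta 1.5 s; alpha 2, beta 2.5 s; alpha 5, beta 1.0 s). The rCBV results agree within 0.01 across shapes; those below are for the first.

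**Following 2.3 (log step).** rCBV = `∫R·k·g / ∫k·g = R`. The ratio returns 3 and 1.5 exactly, whatever the drop. TE cancels in the ratio.

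**Following 7.2.2 as the area of the fractional drop.** rCBV = `∫(1 − exp(−R·k·g)) / ∫(1 − exp(−k·g))`.

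| Control peak drop | Tumour peak drop at R = 3, `1 − (1 − d)^3` | True 3 reads | True 1.5 reads |
|---|---|---|---|
| 10% | 27% | 2.80 (−7%) | 1.47 (−2%) |
| 20% | 49% | 2.60 (−13%) | 1.45 (−4%) |
| 30% | 66% | 2.42 (−19%) | 1.42 (−6%) |
| 40% | 78% | 2.24 (−25%) | 1.39 (−8%) |

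**rMTT.** With a gamma-variate fit to `1 − S/S0` and `MTT = beta·(alpha + 1)`, a true rMTT of 1 reads 1.01 to 1.09 at R = 3 over the three shapes, and 1.00 to 1.02 at R = 1.5. On R2\* curves it returns 1.

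**Between agents.** Suppose the true rCBV is 3 with both agents but the control-region drops differ:

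- equal drops: 0% false difference
- 20% versus 30%: 2.416/2.601 = 0.93, a 7% difference
- 20% versus 40%: 2.240/2.601 = 0.86, a 14% difference
- 10% versus 40%: 2.240/2.796 = 0.80, a 20% difference

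The sign depends on which agent gives the deeper drop, so no direction is claimed.

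**Section 7.4, units.** Area (mm²) times volume (mm³) gives mm⁵, which is not a volume. If pixel count was meant, count × voxel volume is correct and the effect is 0%. Read literally, summed area × voxel volume equals the true volume × in-plane pixel area. If the MPRAGE is the image set used (7.4 does not name one), the printed geometry in 6.3 gives (180/256) × (220/320) = 0.483 mm² at 7T and (256/256) × (192/256) = 0.75 mm² at 3T. The ratio is 0.64, so the same lesion would read 36% lower at 7T from the formula alone.

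**The case against.** The strongest reply is that 7.2.2 is shorthand. Section 2.3 sets out the full method, an experienced perfusion analyst would apply the log step without being told, and on that reading nothing is biased. This is plausible and cannot be excluded. What remains is that 7.2.2 names a different quantity twice, for rCBV and for rMTT, and nothing in Section 7 supplies the conversion or points to 2.3.

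The sizes can also be challenged fairly. The peak drops are assumptions, and the model leaves out leakage and T1 effects, although 1.2.2 expects its agent difference in leaky tumours, where such a model fits least. The figures show how the error arises and over what range; they do not predict what this trial would see.

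Several stronger readings are tempting, and the documents do not support them:

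- **That the primary outcomes are compromised.** CNR in Aims 1 and 2 is defined on signal change, so the missing log step does not touch it.
- **That rCBV would come out below 1.** That follows only from integrating the raw signal itself over the whole scan, which is not a realistic way to run the analysis. Its size also depends on a scan length that is printed inconsistently: 3T item 10 gives 45 volumes at 2.0 s, or 90 s, next to a 6-minute scan time.
- **That 2.3 and 7.2.2 conflict on the reference.** Arterial normalisation in 2.3 and Table 1 belongs to CBV. For rCBV, 2.3 describes contralateral white matter. The open question is only which of the two control regions 7.2.2 means.
- **That differences in coil, voxel size and timing invalidate the 3T–7T CNR comparison.** The plan states openly that sequences are tuned per field strength and that the study is descriptive. How to word the CNR conclusions is a matter of preference.

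**Conclusion.** Section 7.2.2 is wrong as written and contradicts Section 2.3. The consequence is confined to secondary, descriptive outcomes: the rCBV and rMTT summaries and the gadolinium–ferumoxytol comparison of blood volume.

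If 7.2.2 is shorthand, the bias is 0%. If it is followed as the area of the fractional drop, rCBV in a tumour more vascular than its control region is understated: by 7% to 25% at a true 3, and by 2% to 8% at a true 1.5, over assumed control drops of 10% to 40%. That the ratio is pulled towards 1 does not depend on the assumed drops; the amount does. Cancellation between agents would require drops of equal depth, which the plan does not establish. The rMTT effect is smaller, at most +9% in these scenarios.

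The unnamed control region is a real but smaller gap. The Section 7.4 wording is dimensionally wrong, is probably a slip for pixel count, and serves no objective in Section 1. The point is worth fixing before analysis; it is not a threat to the study's main aims.

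**What to change.** 1. **Section 7.2.2, log step.** State that signal is converted to `ΔR2* = −ln(S/S0)/TE`, with S0 the pre-bolus baseline, before both the area calculation and the gamma-variate fit.
2. **Section 7.2.2, control region.** Name one rCBV control region for both agents and both magnets. The contralateral region listed in 7.3 and 7.5 would match the white matter ratio described in 2.3.
3. **Section 7.4 (minor).** Replace the product with number of enhancing voxels × voxel volume, or traced area × slice spacing.
4. **Optional clarification.** The authors could identify the source series for each CNR outcome, and say whether 3T item 10 or item 11 in Section 6.3 is the DSC scan. No particular series needs to be imposed.

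The cost is a few lines of text, with no new scans and no change to acquisition. The log step removes only the non-linearity of the signal. It does not correct gadolinium leakage, so the effect that 1.2.2 sets out to describe stays visible.
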